MRI brain	X ^f						X	All brain scans on protocol are required to be MRI unless MRI is contraindicated, then CT with contrast is acceptable. Subsequently after screening, MRI brain can be performed at any time if clinically indicated per standard of care.

Footnotes defined on last page of this table.

Table 1-1. Schedule of Activities: Cycle 1 only

Procedure ^a	Screening	Treatment Period ^b					As clinically indicated	Notes
		Cycle 1						
Day	(Up to 21 Days Before Day 1)	1	2	8	9	15		
Radiological imaging and tumor assessment ^g	X ^f	Weeks 1 to 48: Q6W (± 1 week) Weeks 49+ Q12W (± 1 week) by BICR per RECIST 1.1					X	Refer to Section 8.3.1 for additional details. For subjects who end study treatment for reasons other than specified in Section 8.3.2, every effort should be made to perform scheduled radiographic imaging (CT/MRI) until radiographic progression.
STUDY TREATMENT AND MONITORING								
Other protocol-required therapy: Dexamethasone		X		X				Refer to Section 6.1.2 for details for pre-treatment with dexamethasone (or equivalent dose of other corticosteroids). Dexamethasone will be administered within 1 hour prior to tarlatamab infusion on days 1 and 8 of cycle 1 only.
Tarlatamab Infusion		X		X		X		

Footnotes defined on last page of this table.

Table 1-1. Schedule of Activities: Cycle 1 only

Procedure ^a	Screening	Treatment Period ^b					As clinically indicated	Notes
		Cycle 1						
Day	(Up to 21 Days Before Day 1)	1	2	8	9	15		
Monitoring post-tarlatamab infusion		X		X			X	Subject will remain at study site for 6 to 8 hours post-infusion at C1D1 and C1D8 Cohabitant (caregiver) support for 24 hours post-infusion and the ability to stay within 1 hour of a hospital for 24 hours is required. Counseling the subject and caregiver on signs and symptoms of CRS and ICANS by a health care provider is required prior to discharge. Subjects return to site on C1D2 and C1D9 for vital signs and physical examination. At subsequent visits, additional monitoring may be recommended post-tarlatamab infusion based on occurrence of CRS, ICANS, or ICANS-related neurological events. Refer to Table 6-1 .
Other protocol-required therapy: IV hydration		X		X				Refer to Section 6.1.2 for details related to IV hydration. IV hydration (1 L normal saline) over 2 to 4 hours following tarlatamab administration.

Page 5 of 5

BICR = Blinded Independent Central Review; C1D1 = cycle 1 day 1; C1D2 = cycle 1 day 2; C1D8 = cycle 1 day 8; C1D9 = cycle 1 day 9;

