CRS = cytokine release syndrome; CT = computed tomography; ECG = electrocardiogram; ECHO = echocardiogram; ECOG PS = Eastern Cooperative Oncology Group Performance Status; EOI = end of infusion; FT4 = free T4; HIV = human immunodeficiency virus; ICANS = immune effector cell-associated neurotoxicity syndrome; IV = intravenous; LDH = Lactate dehydrogenase; MUGA Scan = multigated acquisition scan; MRI = magnetic resonance imaging; NYHA = New York Heart Association; PK = pharmacokinetic; Q6W = every 6 weeks; Q12W = every 12 weeks; RECIST 1.1 = Response Evaluation Criteria in Solid Tumors 1.1; TSH = thyroid-stimulating hormone

^a All procedures and assessments on dosing days are to be completed prior to study drug administration unless otherwise indicated. Assessments should not be performed from the infusion line.

^b Each visit week and day is relative to day 1 of each cycle. Cycle 1 visits have a \pm 1-day window from designated time point unless otherwise specified.

- ^c Additional on-treatment pregnancy testing may be performed at the investigator's discretion if there is suspicion that a female subject is pregnant or per local laws and regulations.
- ^d **If screening local labs are obtained within 48 hours prior to cycle 1 day 1 dose, pre-infusion cycle 1 day 1 samples do not have to be repeated. Where applicable, cycle 1 day 8 and day 15 local labs must be obtained within 48 hours prior to dose (day 8 and day 15). Results must be reviewed prior to study drug administration.**
- ^e **If screening local labs are obtained within 72 hours prior to cycle 1 day 1 dose, the pre-infusion cycle 1 day 1 samples do not have to be repeated. Results must be reviewed prior to study drug administration.**
- ^f Imaging assessments must be within 21 days prior to the first dose of tarlatamab.
- ^g Timing is based on first dose of tarlatamab (C1D1).

Table 1-2. Schedule of Activities: Cycle 2+

Procedure ^a	Treatment Period ^b				EOT ^c	SFU ^d	LTFU ^{e,f}	As clinically indicated	Notes
	Cycle 2		Cycle 3+						
Day	1	15	1	15					
GENERAL AND SAFETY ASSESSMENTS									
Physical examination (including neurological exam)	[X]	X	[X]	X	X	X		X	Physical exam must be completed prior to start of infusion on treatment days. [X]: Must include weight on Day 1 of every cycle.
Vital Signs	X	X	X	X	X	X		X	Includes systolic/diastolic blood pressure, heart rate, respiratory rate, pulse oximetry, and temperature
ECOG PS	X		X		X	X			
ECG					X			X	
Adverse events	continuous							X	

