4.4 Justification for Monitoring

Safety data from clinical Study 20200491 has confirmed that the most common adverse event with tarlatamab is CRS (Ahn et al, 2023). Cytokine release syndrome most frequently occurs after the first two infusions of tarlatamab (cycle 1 day 1 and cycle 1 day 8), is mostly grade 1 to 2 in nature and rarely develops rapidly. The subject incidence of CRS at the 10 mg dose in Study 20200491 was 30.1% (40/133) grade 1, 20.3% (27/133) grade 2 and 0.8% (1/133) grade 3. There were no grade 4 or 5 CRS events in this study. This profile enables **6 to 8 hours** monitoring following the first two tarlatamab doses (cycle 1 day 1 and day 8) and leveraging additional risk mitigation measures: mandatory counseling on signs and symptoms of CRS at time of discharge, a cohabitant for first 24 hours after cycle 1 day 1 and day 8 infusions, and remaining within 1 hour of an appropriate healthcare setting after cycle 1 day 1 and day 8 infusions. Importantly, patients will return to study sites on the day following these infusions for clinical evaluation (ie, cycle 1 day 2 and cycle 1 day 9). Additional detailed guidance for CRS monitoring and mitigation during and following these treatment visits is outlined in protocol Schedule of Activities (Section 1.3) and Section 6.1.

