8.1.2 Treatment Period

Visits will occur per the Schedule of Activities (Section [1.3](#)). The date of the first dose of tarlatamab is defined as day 1. All subsequent doses and study visits will be scheduled based on the day 1 date. On-study cycle 1 day 8 and day 15 visits have a ± 1 day window and all subsequent visits beginning from cycle 2 have a ± 3 day window, unless otherwise specified. Administration of tarlatamab is to be administered last during each visit that it is required. **Subjects will receive study treatment until BICR-confirmed disease progression per RECIST 1.1, death, withdrawal of consent, start of new anticancer therapy, unacceptable toxicity, or end of study as determined by the sponsor (whichever occurs first). Following documented radiographic progression, the subject may remain on study treatment provided criteria are met. Refer to Section [6.1.7](#). Any subsequent (investigator-determined) progressive**

disease per RECIST 1.1 from a new baseline set at initial progression will result in permanent discontinuation of study treatment.

The site principal investigator will make final treatment and subject management decisions. Subjects who discontinue study treatment for reasons other than BICR-confirmed disease progression will continue to have tumor assessments (if clinically feasible) until disease progression is confirmed by BICR.

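### Table 1-1 footnote b does not exempt Days 2 and 9 from its ±1-day window, so on its face the check meant for the day after infusion can fall 2 days (C1D2) or 2 to 3 days (C1D9) later

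*Protocol*

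**What the plan says.** In Table 1-1 (Protocol Section 1.3), footnote b is attached to the treatment-period header above Days 1, 2, 8, 9 and 15. It sets the reference point, "Each visit week and day is relative to day 1 of each cycle", and then gives cycle 1 visits a plus-or-minus "1-day window from designated time point unless otherwise specified". The monitoring row of the same table says "Subjects return to site on C1D2 and C1D9 for vital signs and physical examination" and sets no tighter window. Section 4.1 and Table 6-1 repeat the Day 2 and Day 9 labels, also without a window.

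Section 8.1.2 defines Day 1 as the date of the first dose and adds "All subsequent doses and study visits will be scheduled based on the day 1 date". Its cycle 1 window names two visits only: "On-study cycle 1 day 8 and day 15 visits have a" plus-or-minus 1-day allowance. Days 2 and 9 are not mentioned.

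Section 4.4 explains why 6 to 8 hours on site is enough after the first two infusions. Among the supporting measures it says: "Importantly, patients will return to study sites on the day following these infusions for clinical evaluation", and identifies these returns as C1D2 and C1D9. It then points onward: "Additional detailed guidance for CRS monitoring and mitigation during and following these treatment visits is outlined in protocol Schedule of Activities", and also to Section 6.1.

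**The concern.** Three parts of the protocol give different answers on when these two checks may take place. Footnote b appears to let them move by a day, Section 8.1.2 gives them no window, and Section 4.4 expects them the next day. Sites book visits from the schedule, and Section 8 makes adherence to it mandatory, so the footnote is the text most likely to be applied.

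C1D2 and C1D9 are the only scheduled visits between discharge and the next dosing visit. In Table 8-1 the last timed vital signs on an infusion day are 1 hour after the end of infusion, so these checks also provide the next scheduled set. Required caregiver support and hospital proximity last 24 hours. A check two or more calendar days after infusion comes after both have ended. Section 4.4 says CRS is most frequent after exactly these two infusions. At stake is whether the schedule delivers a safeguard on which the monitoring rationale relies.

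**Working it through.** The plan has no calculated figure to reproduce here. The check lists the permitted days and subtracts.

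**Inputs**
- C1D1 infusion: Day 1 exactly (Section 8.1.2 definition).
- C1D8 infusion: Day 7, 8 or 9 (Day 8 ± 1; footnote b and Section 8.1.2 agree).
- C1D2 check: Day 1, 2 or 3 under footnote b (Day 2 ± 1); Day 2 if only the Section 8.1.2 window applies.
- C1D9 check: Day 8, 9 or 10 under footnote b (Day 9 ± 1); Day 9 if only the Section 8.1.2 window applies.
- Target from Section 4.4: a gap of 1 day.

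**Formula:** gap = check day − infusion day.

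**C1D2 under footnote b:** 1 − 1 = 0; 2 − 1 = 1; 3 − 1 = 2. The latest permitted check is 2 days after infusion.

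**C1D9 under footnote b (gap in days):**

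| Infusion on | Check Day 8 | Check Day 9 | Check Day 10 |
|---|---|---|---|
| Day 7 | 1 | 2 | 3 |
| Day 8 | 0 | 1 | 2 |
| Day 9 | −1 | 0 | 1 |

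The late cases are 2 days (infusion Day 7 with check Day 9, or Day 8 with Day 10) and 3 days (Day 7 with Day 10). The 3-day case needs the infusion a day early and the check a day late. The grid also contains same-day checks and one check before the infusion, which cannot be intended.

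**Section 8.1.2 window only:** C1D2 gives 2 − 1 = 1, as intended. C1D9 gives 9 − 7 = 2, 9 − 8 = 1 and 9 − 9 = 0. The check can still be 2 days late, or coincide with the infusion, because Day 9 is counted from Day 1 while the infusion may move.

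**Check dated from the actual infusion (check day = infusion day + 1):** C1D2 falls on Day 2. C1D9 falls on Day 8, 9 or 10 for an infusion on Day 7, 8 or 9. The gap is 1 in every case.

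In the late cases, the interval from infusion-day vital signs to the next scheduled set grows from 1 calendar day to 2 for C1D2, and to 2 or 3 for C1D9.

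**The case against.** The best reply is that footnote b yields to anything specified elsewhere, and that two places do specify otherwise. Section 4.4 ties the return to the infusion, with C1D2 and C1D9 serving as labels. Section 8.1.2 lists the visits that have a window and leaves these two out. The onward reference in Section 4.4 is to additional guidance, in Section 6.1 as well as Section 1.3, so it does not cancel the next-day return. Applied literally to every column, the footnote would also move Day 1 itself and allow a C1D9 check before its infusion, which suggests that it was not written with Days 2 and 9 in mind.

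Much of this stands. The sponsor's intention is clear. A reader might infer that footnote b settles a late check as compliant; the documents do not support that, because the exception clause leaves room for the next-day reading.

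The reply does not remove the inconsistency. Section 4.4 is a rationale and states no window. Section 8.1.2 does not say that Days 2 and 9 have none. Section 4.1, Table 6-1, Table 8-1 and the Table 1-1 notes use nominal day labels only. Two sites could therefore classify the same Day 3 check differently, and the Day 7 infusion case remains under Section 8.1.2 unless Section 4.4 is taken to govern scheduling.

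**Conclusion.** The point holds as a minor inconsistency in safety monitoring. On the face of the schedule, the C1D2 check may be 2 days after infusion and the C1D9 check 2 to 3 days after, against the 1 day that Section 4.4 expects. Under Section 8.1.2 alone, C1D9 may still be 2 days after. This assumes that a site applies footnote b to every column it heads and does not treat Section 4.4 as an exception.

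Three stronger inferences are not supported:
- **A rate of late checks.** The grid shows what is permitted, not how often it happens. Any share taken from it also depends on whether the same-day and pre-infusion cells are counted.
- **A number of CRS cases missed or found late.** Section 4.4 gives whole-study incidence at 10 mg from Study 20200491, "30.1% (40/133) grade 1, 20.3% (27/133) grade 2 and 0.8% (1/133) grade 3", but the documents give neither onset times nor any rate of window use. The effect on detection cannot be quantified.
- **A gap for restarts after dose delays.** Tables 6-1, 6-3 and 8-1 already carry the cycle 1 monitoring guidance over to them.

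The 6 to 8 hour stay, symptom-free discharge, counseling, caregiver support, hospital proximity and assessments when clinically indicated are all unaffected. So is the ORR analysis.

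**What to change.** In Table 1-1 footnote b, limit the ±1-day window to C1D8 and C1D15, and state that the C1D2 and C1D9 checks take place on the calendar day after the actual C1D1 and C1D8 infusions. Put the same statement in Section 8.1.2. Removing the window from Days 2 and 9 would not be enough by itself; the C1D9 check must also be dated from the actual second infusion.

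The cost is one revised footnote and one added sentence. No visit is added. The downside is that checks held on another day become recorded deviations, and sites must schedule these two infusions so that the following day is staffed, which Section 4.4 already presumes.

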2.1 Study Rationale

Small cell lung cancer (SCLC) is a grave diagnosis, marked by high initial response rates to platinum-based first-line chemotherapy. However, resistance to subsequent treatments quickly emerges, resulting in a median survival of 10 to 12 months post-diagnosis (Rudin et al, 2015). Delta-like ligand 3 (DLL3) is typically intracellular in normal tissues but often overexpressed on the cell surface in most SCLC tumors, making it an attractive target for T-cell therapies (Saunders et al, 2015). Notably, minimal cytoplasmic staining is observed in the brain, pituitary, and pancreatic islets in normal tissues (Study 123377), suggesting the potential for tumor-specific DLL3-targeted therapy.

Tarlatamab (INN; AMG 757) is a novel, extended half-life (HLE) bispecific T-cell engager (BiTE®) designed to direct T effector cells toward DLL3-expressing cells using a tandem single-chain fragment crystallizable (scFc) for prolonged half-life. In an ongoing phase 2 study (Study 20200491), tarlatamab has demonstrated efficacy in SCLC patients with a manageable safety profile (Ahn et al, 2023).

Tarlatamab received accelerated approval from the United States Food and Drug Administration (FDA) for the treatment of adult patients with extensive-stage SCLC with disease progression on or after platinum-based chemotherapy.

Study 20230273 aims to assess tarlatamab's efficacy, safety, tolerability, and pharmacokinetics (PK) in Chinese subjects with advanced SCLC who have progressed on or recurred following 1 platinum-based regimen as first-line (1L) therapy (including a Programmed Cell Death Protein 1 [PD-1]/Programmed Cell Death Ligand 1 [PD-1/PD-(L)1]) and at least 1 other prior line of therapy (re-treatment with a platinum-based regimen is considered a second-line of therapy).

A detailed description of the chemistry, pharmacology, efficacy, and safety of tarlatamab is provided in the investigator's brochure.

2.2 Background

2.2.1 Disease

Small cell lung cancer accounts for 10 to 15% of lung cancer (Rudin et al, 2015), presenting as an aggressive subtype with neuroendocrine differentiation, strongly linked to smoking (Koinis et al, 2016). It exhibits distinct characteristics, including a high

growth rate, rapid doubling time, and early widespread metastasis (Gustafsson et al, 2008).

Approximately 30% of patients have limited disease (LD) confined to one hemithorax, while the majority have extensive disease (ED). Small cell lung cancer is highly responsive to first-line chemotherapy (60% to 70% response rates) and radiation, but resistance rapidly develops for second-line and subsequent therapies after disease recurrence (Byers and Rudin, 2015).

Patients with ED face drug resistance and typically succumb to the disease within a median time of 10 to 12 months from diagnosis (Rudin et al, 2015). First-line treatment for ED-SCLC involves platinum-based chemotherapy, such as platinum etoposide (EP) or platinum irinotecan. Anlotinib is an orally administered tyrosine kinase inhibitor that targets vascular endothelial growth factor receptor (VEGFR), fibroblast growth factor receptor (FGFR), platelet-derived growth factor receptors (PDGFR), and c-kit. It is used in China as the current recommended treatment in third or later line treatment in advanced SCLC, based on the evidence in ALTER1202. This study demonstrates a significant improvement in median progression-free survival (PFS) and a consistent trend in overall survival (OS) (4.0 vs 0.7 months, $P < 0.0001$)/(7.3 vs 4.4 months, $P = 0.006$, respectively) compared with placebo (Shi et al, 2020). However, it shows numerically limited improvements in response rate (objective response rate [ORR] of 4.9%). A median OS of 6.86 months was observed through a real-world study which includes 13 studies, involving 779 patients with SCLC (Xu et al, 2023). There are no approved third-line therapies for relapsed ED-SCLC outside of China, and existing options offer limited OS benefits, with a median OS of 4.4 months (Coutinho et al, 2019). Therefore, there remains a critical medical need for new therapies in third and later-line settings.

2.2.2 Amgen Investigational Product Background: Tarlatamab

BiTE[®] molecules guide T effector memory cells toward target cells, closely mimicking cytotoxic T lymphocyte activation. Tarlatamab, an HLE BiTE[®], combines binding specificities for DLL3 and CD3, genetically fused to the N terminus of the immunoglobulin G scFc region. It is being developed to treat SCLC patients, with its activity dependent on binding to both target cells and T cells. Tarlatamab redirects primed cytotoxic CD8⁺ or CD4⁺ T lymphocytes to eliminate DLL3⁺ cells.

In the phase 1 first in human study (Study 20160323) evaluating the safety, tolerability, and antitumor activity of tarlatamab in SCLC, the available data demonstrate that tarlatamab shows a manageable safety profile and signs of preliminary efficacy.

The pivotal phase 2 study of tarlatamab in patients with relapsed SCLC after 2 lines of prior therapy has confirmed efficacy and benefit/risk ratio (Study 20200491; Ahn et al, 2023). Based on a pre-specified interim analysis in part 1 of the phase 2 Study 20200491, the regimen using a 10 mg target dose Q2W with a 1 mg step-dose was selected as the monotherapy recommended phase 2 dose regimen to balance the efficacy/safety of tarlatamab and to be further evaluated in part 2 and part 3 of the phase 2 Study 20200491, and any subsequent studies for tarlatamab. The primary analysis for the phase 2 Study 20200491 reinforced the selection of 10 mg target dose for tarlatamab studies.

Tarlatamab received accelerated approval from the United States FDA for the treatment of adult patients with extensive-stage SCLC with disease progression on or after platinum-based chemotherapy; please refer to the United States Prescribing Information.

A detailed description of the chemistry, pharmacology, efficacy, and safety of tarlatamab is provided in the investigator's brochure.

2.2.3 Non-Amgen Investigational Product Background

No non-Amgen investigational products will be used in this study.

2.3 Benefit/Risk Assessment

Delta-like ligand 3 is a promising T-cell therapy target is highly expressed in SCLC and other neuroendocrine tumors but minimally expressed in normal tissues. Tarlatamab demonstrated potent T-cell recruitment against DLL3-expressing SCLC cells in vitro and effectively suppressed tumor growth in systemically treated mice. Tarlatamab is expected to offer deeper and more durable responses compared to current and emerging treatments for SCLC.

As of 27 June 2023 (Study 20200491), among patients evaluated for antitumor activity and survival, the median follow-up was 10.6 months in the 10 mg group. An objective response occurred in 40% (97.5% CI, 29 to 52) of the patients. Among patients with an objective response, the duration of response was at least 6 months in 59% (40 of 68 patients). Objective responses at the time of data cutoff were ongoing in 22 of

40 patients (55%) and the median progression-free survival was 4.9 months (95% CI, 2.9 to 6.7); the estimates of OS at 9 months were 68% (Ahn et al, 2023).

Key Safety Information

Based on tarlatamab's ongoing clinical study experience, the key safety information includes the adverse drug reactions of cytokine release syndrome (CRS), immune effector cell-associated neurotoxicity syndrome (ICANS), and neutropenia. Additionally, potential safety issues includes pituitary dysfunction, other neurological events, and tumor lysis syndrome (TLS) which stem from Tarlatamab's mechanism of action and experience with BiTE[®] molecules. For complete details, consult the investigator's brochure.

A comprehensive safety strategy, focusing on CRS, ICANS, neutropenia, other neurological toxicities, pituitary dysfunction, and TLS will be implemented in this study. This includes prevention, continuous monitoring, early recognition, and prompt management. See Section 6.2.2 and Table 6-2 for detailed management recommendations **of the key adverse drug reactions and potential safety concerns of tarlatamab.**

The above benefit-risk assessment supports the conduct of this clinical study.

For additional details on the safety risks, refer to the investigator's brochure.

3. Objective(s) and Endpoint(s)/Estimand(s)

Objectives	Endpoints
Primary	

 Evaluate efficacy of tarlatamab as assessed by objective response rate (ORR) based on blinded independent central review (BICR) per Response Evaluation Criteria in Solid Tumors version 1.1 (RECIST 1.1) 	
 ORR BICR, defined as proportion with best overall response (BOR) of complete response (CR) plus partial response (PR)
Secondary	

 Evaluate efficacy of Tarlatamab as assessed by duration of response (DOR), disease control (DC), and progression-free survival (PFS) based on BICR per RECIST 1.1 	
 DOR, defined as time from the first documentation of objective response (OR) until the first documentation of disease progression or death due to any cause, whichever occurs first. Only subjects who have achieved OR will be evaluated for DOR DC, defined as CR + PR + stable disease (SD) Duration of DC, defined as time from the first documentation of CR, PR, or SD until the first documentation of disease progression or death due to any cause, whichever occurs first. Only subjects who have achieved CR, PR, or SD will be evaluated for Duration of DC PFS, defined as time from enrollment until disease progression or death from any cause, whichever occurs first. Progression will be based on RECIST 1.1.

 Evaluate efficacy of Tarlatamab as assessed by ORR, DOR, DC, and PFS based on investigator assessment per RECIST 1.1 	
 ORR (Investigator) DOR DC Duration of DC PFS

 Evaluate efficacy of Tarlatamab as assessed by overall survival (OS) 	
 OS, defined as time from enrollment until death from any cause

 Evaluate safety and tolerability 	
 Incidence of treatment-emergent adverse events

 Characterize the pharmacokinetics of tarlatamab 	
 Serum concentration of tarlatamab

Evaluate the immunogenicity of tarlatamab	
Incidence of anti-tarlatamab antibody formation
---	---

Estimand(s) for Primary Objective(s)

Objective response rate (ORR) by blinded independent central review (BICR) per RECIST 1.1 in Chinese subjects with advanced SCLC who have progressed on or recurred following 1 platinum-based regimen as 1L therapy (including a PD-1/ PD [L]1) and at least 1 other prior line of therapy (re treatment with a platinum-based regimen is considered a second line of therapy) prior to start of new cancer therapy (while-on-treatment strategy).

4. Study Design

